4.4.2.3.1 OLE Phase

CDP12 analysis cannot be repeated for the OLE phase since EDSS assessments are performed only at every 24 weeks post OLE Week 24.

4.4.2.4 Total Number of T1 Gadolinium–Enhanced Lesions as Detected by Brain Magnetic Resonance Imaging at Weeks 24, 48, and 96

The total number of T1 Gd–enhanced lesions will be calculated as the sum of the individual number of T1 Gd–enhanced lesions at Weeks 24, 48, and 96. Data from other unscheduled assessments will not be included in this summary or analysis.

The same approach to analysis will be applied here as described in Section 4.4.1, “Analysis Methods” section, with the following exceptions:

- In order to account for patients receiving varying numbers of brain MRI scans during the study, the log-transformed number of brain MRI scans received will be included in the model as an “offset” variable for appropriate computation. This approach is preferable to imputation of missing values using the average of non-missing

observations, because only three timepoints would give a high variability in the imputed average values. Additionally, the “offset” variable approach aligns more closely with approaches to analysis used a) in regulatory submissions for other MS therapies, b) for the primary endpoint, and c) in this program’s Phase II study.

- Baseline covariates here will be as follows: baseline Gd lesion (present or not), treatment group, baseline EDSS score (<4.0 vs. ≥4.0), and geographical region (United States vs. ROW).

Sample SAS code can be found below (SAS code is regarded as “draft” until fully validated at the analysis stage):

```
proc genmod data=MRIT1;
  class ARMCD REGION BEDSSCAT BGDLESFL;
  model N MRIT1 = ARMCD REGION BEDSSCAT BGDLESFL /
  offset=MRILOG link=log dist=negbin type3;
  lsmeans ARMCD / exp cl;
  ods output lsmeans=ls;
  ods output ParameterEstimates=est;
run;
```

If the model fails to converge due to high number of zero T1 lesion counts, a logistic regression model will be performed on Gd lesion (present or not) adjusted for the same baseline variables. Patients withdrawn from treatment and having no T1 lesions: those withdrawn because of lack of efficacy or death are considered as having T1 lesions; otherwise, it will be considered a missing observation:

```
proc logistic data=MRIT1;
  class ARMCD REGION BEDSSCAT BGDLESFL;
  model N MRIT1 CAT = ARMCD REGION BEDSSCAT BGDLESFL;
  oddsratio ARMCD /cl=wald;
  ods output OddsRatiosWald = oddsr;
run;
```

4.4.2.4.1 OLE Phase

This analysis will be modified to include data collected during the OLE period. This analysis will be an exploratory analysis and will be performed for each visit from baseline up to the last mature visit. The last mature visit is defined as the visit where the majority of patients have completed prior to the data cutoff date. Of note, MRI is only collected once a year during OLE.

Adjusted rate and adjusted rate ratio based on the negative binomial models may not be estimable due to low number of lesions. Hence, unadjusted rate (total number of lesions divided by number of scans), unadjusted rate ratio and corresponding confidence intervals based on the exact poisson test will be presented.

4.4.2.5 Total Number of New and/or Enlarging T2 Hyperintense Lesions as Detected by Brain Magnetic Resonance Imaging at Weeks 24, 48, and 96

The total number of new and/or enlarging T2 lesions will be calculated as the sum of the individual number of new and/or enlarging lesions at Weeks 24, 48, and 96. Data from other unscheduled assessments will not be included in this summary or analysis.

- The same approach to analysis will be applied here as described in Section 4.4.2.4, with the following exception.
- Baseline covariates here will be as follows: baseline T2 lesion count, treatment group, baseline EDSS score (<4.0 vs. ≥4.0) and geographical region (United States vs. ROW).

Sample SAS code can be found below (SAS code is regarded as “draft” until fully validated at the analysis stage):

```
proc genmod data=MRIT2;
  class ARMCD REGION BEDSSCAT;
  model N MRIT2 = ARMCD REGION BEDSSCAT BT2LES /
  offset=MRILOG link=log dist=negbin type3;
  lsmeans ARMCD / exp cl;
  ods output lsmeans=ls;
  ods output ParameterEstimates=est;
run;
```

If the model fails to converge due to a high number of zero T2 lesion counts, a logistic regression model will be performed on new/enlarging T2 lesion (present or not) adjusted for the same baseline variables. Patients withdrawn from treatment and having no T2 lesions: those withdrawn due to lack of efficacy or death are considered as having T2 lesions; otherwise, it will be considered a missing observation.

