1. BACKGROUND

Studies WA21092 and WA21093 are two Phase III studies with identical study design. This Statistical Analysis Plan (SAP) describes the analyses that will be performed for each study independently. The analyses will be conducted in exactly the same way for both studies; therefore, only one SAP has been written to be applied to both studies. The analysis of some secondary efficacy endpoints will necessitate the pooling of data from both studies in order to have sufficient statistical power to detect relevant treatment differences. Analyses of pooled data are described separately in the “Pooled SAP.”

Study WA21493 is an ongoing double-blind, double-dummy, parallel-group, Phase II study of the efficacy and safety of ocrelizumab compared with interferon beta-1a intramuscular (IM) (Avonex) in patients with relapsing remitting multiple sclerosis (RRMS). The study was unblinded in November 2009 and has an open-label phase that is ongoing. After 24 weeks of treatment, both doses of ocrelizumab (600 mg and 2000 mg) demonstrated a strong effect with a highly statistically significant reduction versus placebo in signs of paraclinical disease activity as measured by the number of gadolinium (Gd)-enhancing brain lesions in magnetic resonance imaging (MRI), the primary endpoint of the study, at Weeks 12, 16, 20, and 24. Compared with placebo, this represents a relative reduction in the number of lesions of 89% and 96%, for the 600-mg and 2000-mg ocrelizumab groups respectively. In addition, a statistically significant reduction in the annualized relapse rate (ARR) was observed with both ocrelizumab doses compared with placebo. Moreover, both ocrelizumab doses were superior to the active comparator, Avonex, for both the MRI primary endpoint and the ARR.

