4.4.2.8.1 OLE Phase

This analysis will be modified to include data collected during the OLE period. This analysis will be an exploratory analysis and will be performed for each visit from baseline

up to the last mature visit. The last mature visit is defined as the visit where the majority of patients have completed prior to the data cutoff date. Of note, MRI is only collected once a year during OLE.

Adjusted rate and adjusted rate ratio based on the negative binomial models may not be estimable due to low number of lesions. Hence, unadjusted rate (total number of lesions divided by number of scans), unadjusted rate ratio and corresponding confidence intervals based on the exact poisson test will be presented.

4.4.2.9 Change in Multiple Sclerosis Functional Composite Scale Score from Baseline to Week 96

There are three primary measures in a MSFC score: 1) Timed 25-Foot walk; 2) 9-Hole Peg Test (9-HPT); and 3) Paced Auditory Serial Addition Test (PASAT-3 version). The MSFCS is based on the concept that scores for these three dimensions (arm, leg, and cognitive function) are combined to create a single score (the MSFC) that can be used to detect change over time in a group of patients with MS. Since the three primary measures differ in what they actually measure (time for the 9-HPT and 25-Foot Timed Walk, but number of correct answers for the PASAT-3), a common metric for these variables has been used to create a composite score for the three different measures. Z-score was selected for this purpose. The results from each of these three tests are transformed into Z-scores and averaged to yield a composite score for each patient at each timepoint.

$$\text{MSFC Score} = \{Z_{\text{arm, average}} + Z_{\text{leg, average}} + Z_{\text{cognitive}}\} / 3.0$$

Where Zxxx = Z-score

The following are MSFC components:

- Trial 1, Timed 25-Foot Walk
- Trial 2, Timed 25-Foot Walk
- Trial 1, Dominant Hand, 9-HPT
- Trial 2, Dominant Hand, 9-HPT
- Trial 1, Non-Dominant Hand, 9-HPT
- Trial 2, Non-Dominant Hand, 9-HPT
- PASAT-3

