For each treatment group, the incidence count for each adverse event PT will be defined as the number of patients reporting at least one treatment emergent occurrence of the event. The incidence rate will be calculated as the incidence count divided by the total number of patients in the population. Each table will also present the overall number of patients experiencing at least one adverse event and the total number of adverse events reported (multiple occurrences of the same adverse event in 1 patient will be counted only once).

The number of patients who experienced a related adverse event will be summarized by system organ class (SOC) and PT. Adverse events will be summarized by SOC and PT by intensity grade. Multiple occurrences of the same event within a patient will be counted once at the greatest intensity/highest grade for this PT. For adverse events leading to death, the most extreme intensity will be overwritten by Grade 5 (death). Any adverse events and the SOC overall rows of the summary table will count patients according to adverse events by intensity/grades.

All patient deaths, regardless of treatment received, will be listed.

Serious adverse events will be defined as all serious adverse events including serious MS relapses and serious IRRs. The number of patients who experienced a serious adverse event will be summarized by SOC and PT. Related serious adverse events will be summarized by SOC and PT. Additionally, the most frequent serious adverse events ($\geq 1\%$) will be presented by PT.

A separate listing with relapses considered as serious adverse events will be presented.

A patient may experience an adverse event that leads to the discontinuation of their study treatment. Discontinuation of study treatment for an adverse event may not necessarily lead to discontinuation from the study because patients can enter the safety follow-up periods of the protocol. Only adverse events that led to the discontinuation of

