4.6.3.1 Selected Adverse Events

Infection

Infections will be defined from the adverse event data using the MedDRA SOC of “Infections and Infestations.” During Primary CSR, adverse events that are reported as an infection by the investigator will also be included.

During Primary CSR, an infection has been defined as serious if the event is a serious adverse event or if the non-serious infection was treated with an IV anti-infective. For subsequent reporting, an infection has been defined as serious if the event is a serious adverse event.

The number of infections and serious infections per 100 patient-years will be calculated and summarized separately. The ninety-five percent CI of the incidence rates will be calculated using exact method based on Poisson distribution.

Summary of infections will be presented by SOC and PT, severity, and Dose. Similar summary tables will be also produced by serious infections.

Summary tables of infections and serious infections by pathogen information codes as well as listing of infections/serious infections with pathogen codes will be produced.

Infusion-Related Reactions

An IRR and its corresponding symptoms are collected on the dedicated eCRF.

The symptom(s) of an IRR and the IRR itself may be of different intensities. As other symptoms can be recorded as free-text on the eCRF page, symptoms will be coded in the MedDRA and summarized by PTs.

IRRs are categorized by the time of the event occurring (1) during the infusion, (2) after completion of the infusion while patient is in the clinic, and (3) within 24 hours of completion of the infusion and patient is not in the clinic. The number and percentage of patients with at least one IRR will be presented by infusion (patients with multiple events within an infusion will count only once). In addition, the total number of IRRs will be

summarized (multiple events will be counted). The total and percentage (based on the total number of patients with at least one IRR) will be summarized by most extreme intensity.

IRRs will be summarized by intensity and by infusion. For multiple events within a patient, the most extreme intensity will be taken.

Symptoms of IRR and symptoms of serious IRR will also be presented by infusion. This analysis will be produced for both the controlled treatment period and the OLE period.

The number of patients with at least one IRR, the total number of IRRs, and the number of IRRs will be summarized by the time of events.

Pregnancies

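### If lesion or infection counts are overdispersed, the exact Poisson intervals planned for by-visit lesion rate ratios and for the overall infection rate are too narrow

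*SAP*

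**What the plan says.** SAP 4.4.2.4.1 (gadolinium-enhancing T1 lesions) first says that the adjusted negative binomial rate and rate ratio "may not be estimable due to low number of lesions". It then says that the "unadjusted rate ratio and corresponding confidence intervals based on the exact poisson test will be presented". The analysis "will be performed for each visit from baseline up to the last mature visit", with no rule confining the exact method to visits with few lesions. Sections 4.4.2.5.1 (new or enlarging T2 lesions) and 4.4.2.8.1 (chronic black holes) repeat this; in the latter, "confidence intervals based on the exact poisson test will be presented".

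For the double-blind period, SAP 4.4.2.4, 4.4.2.5 and 4.4.2.8 model the same lesion types, summed over Weeks 24, 48 and 96, with a negative binomial model and a log number-of-scans offset.

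For safety, SAP 4.6.3.1 says: "The number of infections and serious infections per 100 patient-years will be calculated and summarized separately". The 95% "CI of the incidence rates will be calculated using exact method based on Poisson distribution". The general adverse event text in 4.6.3 says that "multiple occurrences of the same adverse event in 1 patient will be counted only once". Section 4.6.3.1 does not say whether that rule carries over to the infection rate.

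**The concern.** The reason for leaving the negative binomial model is conditional, but the switch is unconditional. An exact Poisson interval sets the variance of each patient's count equal to its mean. One patient can contribute several lesions on a scan, and the SAP allows for extra-Poisson variation when it models the summed counts. It also allows for dependence within patients in the yearly relapse analysis of the extension, which uses a GEE Poisson model (4.4.1). The by-visit lesion intervals drop that allowance even where counts are large enough to keep it.

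The infection rate raises the same question, because one patient can have several infections. Infection is listed as an identified risk of the drug (protocol 7.3.1.1), so the interval around its rate should not look tighter than the data allow. What is at stake is the stated precision of exploratory lesion ratios and of one descriptive safety rate.

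**Working it through.** **What the documents supply.** They attach no figure to these intervals beyond the nominal 95% for infections. The one related published interval is the Phase II infection rate in protocol 2.1.4.1, 92.41 per 100 patient-years (76.59 to 111.5). Read as a log-scale Poisson interval, its standard error is ln(111.5/76.59)/3.92 = 0.0958, so events = 1/0.0958² ≈ 109 and patient-years = 109/0.9241 ≈ 118. The serious-infection interval (3.39; 1.27 to 9.04) gives ln(9.04/1.27)/3.92 = 0.501, so 4 events and again 118 patient-years. Both have pure Poisson width, so neither tells us anything about dispersion.

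**Assumptions.** Lesions: 700 patients per arm with one scan per visit (the pooled studies plan 800 per arm), dispersion k between 1 and 10, and per-scan rates as shown. Infections: 400 patients per arm followed for 96 weeks (1.84 years) at the Phase II rate, with k between 0.3 and 1.0.

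**Lesion rate ratio.** With patient variance μ(1 + kμ), the variance of the log rate ratio is (1/n)(1/μ₁ + 1/μ₂ + 2k). The Poisson interval omits 2k. The true-to-Poisson width factor is therefore √[1 + 2k/(1/μ₁ + 1/μ₂)], which is √(1 + kμ) when the arms are equal. Coverage is simulated for the conditional exact (Clopper-Pearson) interval.

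| Lesions per scan | k | Width factor | Coverage |
|---|---|---|---|
| 0.3 vs 0.3 | 1 | √1.3 = 1.14 | 92% |
| 0.3 vs 0.3 | 3 | √1.9 = 1.38 | 86% |
| 0.3 vs 0.3 | 10 | √4 = 2.00 | 67–68% |
| 0.1 vs 0.1 | 1 | √1.1 = 1.05 | 94% |
| 0.1 vs 0.1 | 10 | √2 = 1.41 | 85–86% |
| 0.033 vs 0.3 | 3 | √(1 + 6/33.6) = 1.09 | 94–95% |
| 0.033 vs 0.3 | 10 | √(1 + 20/33.6) = 1.26 | 90–91% |
| 0.011 vs 0.1 | 3 to 10 | 1.03 to 1.09 | 97–95% |
| 0.02 vs 0.02 | 3 to 10 | 1.03 to 1.10 | 96–95% |

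The unequal-arm rows borrow the 89% Phase II reduction versus placebo (SAP section 1), rounded. With k = 0, coverage at 0.3 vs 0.3 is 95.3% (800 per arm), so without overdispersion there is no defect.

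**Sparse visits.** Holding k constant as the mean falls removes clustering. At μ = 0.005 and k = 10, the chance of any lesion is 1 − 1.05^(−0.1) = 0.00487, so an affected scan carries 0.005/0.00487 = 1.03 lesions on average. If affected scans instead carry a mean of 2 to 3 lesions (assumed), simulated coverage of the exact interval at sparse visits is about 90% to 73%. As a rough analytic check, exactly m lesions per affected scan at a sparse visit inflates the width by √m, that is 1.41 for m = 2 and 1.73 for m = 3.

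**Overall infections.** The mean per patient is 0.9241 × 1.84 = 1.70. The width factor √(1 + 1.70k) is 1.23, 1.36 and 1.64 for k = 0.3, 0.5 and 1.0; simulated coverage is about 89%, 85% and 77–78%. If each infection term counts once per patient, coverage is 94.5%, 91.6% and 85.8% under an assumed mix of terms.

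**Serious infections.** The mean is 0.0339 × 1.84 = 0.062. Coverage stays at about 95% for k up to 1.0.

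**The case against.** The strongest reply is that nothing in the documents shows overdispersion at any given visit, and that few visits may be affected. In the extension both arms receive ocrelizumab (SAP 4.2), and the Phase II mean gadolinium-lesion count on the 600 mg regimen was 0 at Week 144 (protocol 2.1.4.2). The clearest non-sparse example, gadolinium lesions at baseline, compares the arms before treatment. With one arm sparse, the table shows little loss. The double-blind lesion endpoints already have negative binomial inference, and one method across all visits keeps a table readable. For infections, 4.6.3.1 says explicitly that multiple infusion reactions are counted but says nothing similar for infections, so the count-once rule may apply.

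Much of this stands. It makes the point conditional and limits its reach, but it does not justify using the exact method where the SAP's reason for it is absent.

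A reader might infer in the other direction that near-zero visits are safe, or that a sandwich interval restores 95% everywhere. Both hold only under a negative binomial with constant dispersion. With 2 to 3 lesions per affected scan, the rule proposed below gave about 85% to 95% at sparse visits. With 2 to 4 lesions and only 0.2% of scans affected, it gave 92% to 77%.

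**Conclusion.** The concern holds in conditional form: if counts are overdispersed, the exact Poisson intervals overstate precision. For lesions, overdispersion is what the SAP's own model for the summed counts allows for. For infections, it is an assumption about differences between patients and about whether repeats are counted.

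The size rests on assumed dispersion and rates. At non-sparse visits it runs from minor (94% coverage at 0.1 per scan, dispersion 1) to large (67% at 0.3 per scan, dispersion 10). Sparse visits can be declared neither affected nor unaffected without knowing how lesions cluster. Overall infections lose coverage to about 89% to 78% if repeats count, and lose less or nothing if they do not. Serious infections are not materially affected.

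A reader might take this as a threat to the trial's conclusions. The documents do not support that: the lesion outputs are labelled exploratory, the safety data are summarized descriptively (SAP 4.6), and the primary and hierarchical tests do not use these intervals. It is a small correction worth making.

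**What to change.** In SAP 4.4.2.4.1, 4.4.2.5.1 and 4.4.2.8.1:

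- At each visit where both arms have at least one lesion, report the unadjusted rate ratio from a Poisson model with arm, a log number-of-scans offset and patient-level sandwich variance. This model can be fitted whenever both totals are positive, which meets the SAP's estimability worry. Under constant-dispersion negative binomial counts, the full rule simulated at 94–97% coverage for rates of 0.01 to 1.0 per scan.
- Where an arm has no lesions, keep the exact Poisson interval, labelled as a fallback that assumes independent lesions.
- State that at very sparse visits neither interval is guaranteed to reach 95% if lesions cluster in few patients.

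In SAP 4.6.3.1, use a sandwich or negative binomial interval with a log patient-years offset for the overall infection rate, and state whether repeat infections in a patient are counted. The exact interval may stay for serious infections.

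The cost is a few lines of text and code and no new data; SAP 2.4 still lists the final study report as planned. The drawbacks are somewhat wider intervals, two interval methods in one table, and a mismatch with interim outputs already produced.

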4.4.2.5.1 OLE Phase

This analysis will be modified to include data collected during the OLE period. This analysis will be an exploratory analysis and will be performed for each visit from baseline up to the last mature visit. The last mature visit is defined as the visit where the majority of patients have completed prior to the data cutoff date. Of note, MRI is only collected once a year during OLE.

Adjusted rate and adjusted rate ratio based on the negative binomial models may not be estimable due to low number of lesions. Hence, unadjusted rate (total number of lesions divided by number of scans), unadjusted rate ratio and corresponding confidence intervals based on the exact poisson test will be presented.

4.4.2.6 Proportion of Patients Who Have Confirmed Disability Improvement Sustained for at Least 12 Weeks with the Initial Event of Neurological Improvement Occurring during the 96-Week, Double-Blind, Double-Dummy Treatment Period

This endpoint will be analyzed only for the subgroup of patients with a baseline EDSS score ≥2.0. Exactly the same approach to data derivation will be used for disability improvement as for disability progression (refer to Section 4.4.2.3, although note that here the endpoint is a binary improved/not improved variable, rather than a time-to-event endpoint). In particular, the same approach to the timing of the confirmation of disability improvement will be applied as for disability progression. The baseline EDSS is the average of the screening EDSS score and the score of the baseline visit, without rounding. For patients with a baseline EDSS score ≥2 and ≤5.5, disability improvement is defined as a reduction in EDSS score ≥1.0 compared to baseline EDSS score. For patients with a baseline EDSS score >5.5, disability improvement is defined as a

reduction in EDSS score of ≥ 0.5 . All patients without disability improvement will be counted as not improved, independent of follow-up time

This analysis requires both Studies WA21092 and WA21093 to be combined to have sufficient statistical power to detect relevant treatment differences. In the study-level analysis, the p-value for this treatment comparison will be interpreted as non-confirmatory.

The proportions in treatment groups will be compared using the Cochran-Mantel-Haenszel (CMH) χ^2 test stratified by geographical region (United States vs. ROW), and baseline EDSS score (< 4.0 vs. ≥ 4.0).

Sample SAS code can be found below (SAS code is regarded as “draft” until fully validated at the analysis stage):

```
proc freq data=CDI12;
  tables REGION*BEDSSCAT*ARMCD*CDI12 / cmh;
  ods output CMH=pval;
  ods output CommonRelRisks=risks;
run;
```

